6.5. Adjustments for Multiple Comparisons

A Hommel multiple testing procedure will be utilized to maintain an overall type I error rate of 0.025 for the three hypotheses tested as part of the secondary objective³. Testing for this objective will be performed if the primary objectives are met. The Hommel procedure is a "step-up" method of error adjustment.

The three hypotheses associated with the secondary objective (see 6.2.3) will be denoted here as H(1), H(2), and H(3). H(1), H(2) and H(3) denote the null hypothesis for change in AFEQT, change in SF-12 mental component, and SF-12 physical component. For each of the hypotheses, p-values will be calculated and sorted $p(1) < p(2) < p(3)$. The decision rule to accept or reject each hypothesis will follow the step-up algorithm, where $\alpha=0.025$.

Step 1: If $p(3) > \alpha$, accept H(3) and go to Step 2, otherwise reject all hypotheses and stop

Step 2: If $p(2) > \alpha/2$, accept H(2) and go to Step 3, otherwise reject all remaining hypotheses and stop

Step 3: If (1) $\alpha/2 < p(2) \leq 2\alpha/3$ and $p(1) \leq \alpha/2$ or (2) $p(1) \leq \alpha/3$, reject H(1); otherwise accept H(1).

³ Hommel, G. A stagewise rejective multiple test procedure based on a modified Bonferroni test. *Biometrika* 1988; 75, 383-386.

Demographic strata with <5 events will be combined with other strata if the resulting combination is still deemed analytically meaningful, or may be ignored due to information sparsity. Age will be calculated as [year of baseline date – year of birth] as the case report form does not collect the exact date of birth for a subject. For subgroup analysis, age will be divided into quartiles. The log-rank test will be utilized. If the overall log-rank test of equality over strata is significant for strata with more than two levels, Tukey's range test will be used to adjust type I error for the comparison between multiple subgroups. Subgroup analyses will be performed in the same datasets in which the corresponding primary or secondary objectives are analyzed.

In addition to subgroup analyses by demographic variables, there are eight pre-specified subgroup analyses that will be performed:

- by Left Atrial Diameter (LAD) at the most recent measurement prior to the procedure;
- by duration of persistent AF, measured in terms of months prior to the procedure;
- by number of prior failed AAD's
- by history of hypertension (binary)
- by history of cardioversion (binary)
- by Subjects with baseline ECG performed within 30 days of index ablation versus > 30 days.
- by body mass index (BMI) > 40 versus ≤ 40
- Major inclusion criteria: Subjects with symptomatic persistent AF documented by two documented ECGs versus subjects with symptomatic persistent AF documented by one ECG and a doctor note indicating the patient had symptoms consistent with AF

The last three subgroup analyses in the list above (by ECG within 30 days of baseline, by BMI > 40, and by major inclusion criteria documentation method) were added based on FDA's correspondence related to STOP Persistent AF IDE Study (G160177/S007) received by Medtronic on January 10, 2018. Each of these subgroups will be analyzed using nonparametric Kaplan-Meier methods like the demographic variables in the manner described above. LAD will be divided into quartiles, while divisions of prior persistent AF duration and prior failed AAD's into discrete bands will be determined after examination of the distribution of these variables in the data.

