17.4. Secondary Objective

The secondary objective, Quality of Life, will be evaluated to gain additional information about the performance of the Arctic Front Advance Cardiac CryoAblation catheter.

There are three hypotheses tested in the objective, hypothesis tests for AFEQT questionnaire, the physical component score of the SF-12 questionnaire, and the mental component score of the SF-12 questionnaire. A Hommel multiple testing procedure will be utilized to maintain an overall type I error rate of 0.025 for this objective²².

The Hommel procedure is a stepwise procedure and will be implemented following the below.

The three hypothesis will be defined as H(1), H(2), and H(3). For each of the hypotheses, p-values will be calculated and sorted $p(1) < p(2) < p(3)$. The decision rule to accept or reject each hypothesis will follow the step-up algorithm, where $\alpha=0.025$:

Step 1: If $p(3) > \alpha$, accept H(3) and go to Step 2, otherwise reject all hypotheses and stop

Step 2: If $p(2) > \alpha/2$, accept H(2) and go to Step 3, otherwise reject all remaining hypotheses and stop

Step 3: If (1) $\alpha/2 < p(2) \leq 2\alpha/3$ and $p(1) \leq \alpha/2$ or (2) $p(1) \leq \alpha/3$, reject H(1); otherwise accept H(1)

17.4.1. Secondary Objective: Quality of Life - Atrial Fibrillation Effect on Quality-of-life (AFEQT) and SF-12 Questionnaires

Demonstrate an improvement in quality of life between baseline and 12 months as measured by the AFEQT and SF-12 questionnaires.

²² Hommel, G. A stagewise rejective multiple test procedure based on a modified Bonferroni test. *Biometrika* 1988; 75, 383-386.

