2.0	07-NOV-2018	
Version 2 includes one change. In the Secondary Objective analysis methods, the following sentence was added "H(1), H(2) and H(3) denote the null hypothesis for change in AFEQT, change in SF-12 mental component, and SF-12 physical component.". This sentence was added based on FDA Study design consideration from FDA STOP Persistent AF IDE approval letter dated November 11, 2016.
	
[name], Sr. Principal Statistician, CRHF

3.0	15-NOV-2018	
Version 3 of the SAP defines an interim analysis. The addition of the interim analysis was suggested by the FDA in feedback on Q181709 dated October 17, 2018. The interim analysis methods have been added to Appendix A.
 
An interim analysis was not previously included in SAP version 1 and 2 or the study protocol. Interim primary efficacy and primary safety objectives and statistical performance criteria have been defined.
 
The interim analysis plan also includes all secondary and ancillary objectives for the study. Due to interim follow-up, some of the objectives have been modified to account for interim this (ie. not all subjects will have complete 12 month data).
 
The intent of the version is to pre-defined all objectives and analyses (interim primary efficacy and primary safety, secondary and ancillary) that will be reviewed during an interim analysis.
 
The timing of this interim analysis will occur when at least 70% of follow-up has occurred. This timing is projected to coincide with the projected last 6-month visit date. It is estimated that 75% of the total expected follow-up will be available at the timing of this analysis.
 
Appendix A has been added and includes all the details of the interim analysis.
 
Additional changes include three new defined subgroups:
 
 Subjects with symptomatic persistent AF documented by two documented ECGs versus subjects with symptomatic persistent AF documented by one ECG and a doctor note indicating the patient had symptoms consistent with AF Subjects with body mass index (BMI) > 40 versus ≤ 40. 	
[name], Sr. Principal Statistician, CRHF

STOP Persistent AF Statistical Analysis Plan

08-JUL-2019

Version 4.0

Page 4 of 25

Medtronic

Version	Date	Summary of Changes	Author(s)/Title

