6.2.4.1. AFEQT

The AFEQT questionnaire will be utilized for this objective. The questionnaire is an atrial fibrillation specific health-related quality of life questionnaire to assess the impact of AF on a subject's life. The overall score ranges from 0 – 100, with 0 corresponds to complete disability and 100 corresponds to no disability.

Hypothesis

The following hypothesis will be tested in a one-sided test at the 0.025 significance level:

$$H_0: \Delta AFEQT = 0$$

$$H_a: \Delta AFEQT > 0$$

Where $\Delta AFEQT$ is the change in AFEQT score from baseline to 12 months.

Analysis Methods

Change in AFEQT score is defined as 12-month AFEQT score minus baseline AFEQT score. Change in AFEQT scores will be assessed utilizing a one-sample t-test. A two-sided 95% confidence interval will be calculated based on the t-distribution.

Additionally, summary statistics (e.g. mean, SD, median, range) and graphical methods will be used to summarize the change in AFEQT scores from baseline through 12 months. The outcome variable for this objective requires both a baseline and a follow-up assessment of AFEQT scores with answers for all questions. Analysis will be performed on the mITT dataset for those subjects that have completed at least 50% of the questions for each subscale at baseline and 12-months.

Performance criteria

If the p-value from the one-sample t-test after adjusting for the Hommel procedure is < 0.025 , the objective will be considered met.

Additional Analyses

The AFEQT questionnaire has three subscale scores, Daily Activities Subscale, Treatment Concern, and Treatment satisfaction. Each subscale ranges from 0 – 100, where 0 corresponds to low quality-of-life and 100 corresponds to high quality of life.

Change in AFEQT subscale score is defined as 12-month AFEQT subscale score minus baseline AFEQT subscale score. A two-sided 95% confidence interval will be calculated based on the t-distribution.

² Hommel, G. A stagewise rejective multiple test procedure based on a modified Bonferroni test. *Biometrika* 1988; 75, 383-386.

answered. Analysis will be performed on complete cases within the mITT dataset, in subjects that have completed both a baseline and 12-month questionnaire.

Performance criteria

If the p-value from the one-sample t-test after adjusting for the Hommel procedure is < 0.025 , the objective will be considered met.

Additional Analyses

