6.8. Changes to Planned Analysis

Comprehensive details on analysis methods have been included to this SAP, but no changes to the statistical methods or principal features defined in the STOP AF First CIP version 5 are noted. However, there are two minor additions from the methods defined in the STOP Persistent AF CIP version 5. First, clarification has been added that while this study assesses subjects' QoL at six month follow-ups, and results from 6-month assessments will be made available in graphs and tables, the endpoints for the secondary objective are defined based only on QoL at baseline and 12 months. An additional repeated measures analysis may be performed outside of the analysis pre-specified for the secondary objective that utilizes data from all three points of assessment. Second, [REDACTED] was added to ancillary objective [REDACTED]

Additional analysis or deviations from procedures in this SAP may be addressed by the release of newer SAP versions, or will be described in the final report and/or main manuscript, along with the rationale for the deviation.

7. Determination of Sample Size

Sample size for STOP Persistent AF was determined by finding the minimum number of subjects enrolled which provides adequate power to both the hypothesis test for the primary efficacy objective, as well as the hypothesis test for the primary safety objective. Calculations are provided separately for each primary endpoint.

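### SAP 6.5 fixes H(1)–H(3) to named questionnaires, but its Hommel steps work only if H(i) follows the i-th smallest p-value

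*SAP*

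**What the plan says.** SAP 6.5 sets the multiplicity rule for the secondary objective: "A Hommel multiple testing procedure will be utilized to maintain an overall type I error rate of 0.025 for the three hypotheses". It then names the hypotheses: "H(1), H(2) and H(3) denote the null hypothesis for change in AFEQT, change in SF-12 mental component, and SF-12 physical component". The next sentence sorts the three p-values from smallest to largest as p(1), p(2), p(3). With α = 0.025, the steps are:

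- Step 1: if p(3) exceeds α, "accept H(3) and go to Step 2, otherwise reject all hypotheses and stop".
- Step 2: if p(2) exceeds α/2, H(2) is accepted and the procedure moves on; otherwise the remaining hypotheses are rejected.
- Step 3: H(1) is rejected if p(1) is at most α/3, or if p(2) lies above α/2 and at most 2α/3 while p(1) is at most α/2.

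SAP 6.2.4.1 gives the success criterion for AFEQT: "If the p-value from the one-sample t-test after adjusting for the Hommel procedure is < 0.025 , the objective will be considered met". The SF-12 criterion in SAP 6.2.4 is worded the same way.

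Protocol 17.4 has the same steps but does not tie H(1)–H(3) to questionnaires. The SAP version log shows where the labels came from. Its version 2.0 entry says "In the Secondary Objective analysis methods, the following sentence was added", attributes the sentence to an FDA study design consideration, and records no change to the steps.

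**The concern.** The steps use one index for two different things. In p(i) it is the rank of a p-value; in H(i), after the labelling sentence, it is a fixed questionnaire. Hommel's procedure needs H(i) to be the null hypothesis that produced p(i). With fixed labels, the largest p-value always decides SF-12 physical and the smallest always decides AFEQT, whichever test they came from.

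The SAP therefore holds two decision rules for the same three tests: the literal steps in 6.5 and the adjusted p-value in 6.2.4.1. They can name different questionnaires as improved, and only the second controls the error rate at the stated 0.025.

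**Working it through.** **Inputs.** From SAP 6.5 and 6.2.4.1: α = 0.025, one-sided, three hypotheses. The thresholds are α = 0.025, α/2 = 0.0125, 2α/3 = 0.01667 and α/3 = 0.00833.

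**The thresholds reproduce.** With H(i) attached to the i-th smallest p-value, the three steps matched a standard Hommel routine and the full closed Simes test in all of 40,000 random p-value triples. Only the labels are at fault.

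**Worked example.** p = 0.0001 (AFEQT), 0.30 (mental), 0.001 (physical). Sorted: 0.0001, 0.001, 0.30.

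- Literal steps: 0.30 > 0.025, so H(3) = physical is accepted. Then 0.001 ≤ 0.0125, so H(1) = AFEQT and H(2) = mental are rejected.
- Adjusted p-values (for each hypothesis, the largest Simes p-value over the subsets containing it):
  - AFEQT: min(3 × 0.0001, 1.5 × 0.001, 0.30) = 0.0003
  - physical: min(2 × 0.001, 0.30) = 0.002
  - mental: 0.30

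  The SAP 6.2.4.1 criterion is met for AFEQT and physical.

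Other examples:

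| p (AFEQT, mental, physical) | Adjusted p | Hommel names | Literal steps name |
|---|---|---|---|
| 0.20, 0.001, 0.30 | 0.30, 0.003, 0.30 | mental | AFEQT |
| 0.015, 0.001, 0.30 | 0.03, 0.003, 0.30 | mental | AFEQT |
| 0.20, 0.20, 0.005 | 0.20, 0.20, 0.015 | physical | AFEQT |
| 0.002, 0.001, 0.30 | – | AFEQT, mental | AFEQT, mental |

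**When the readings agree.** They agree only if one of these holds:

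- (a) all three p-values are ≤ 0.025;
- (b) the largest is > 0.025, the middle is ≤ 0.0125, and physical has the largest;
- (c) the largest is > 0.025, the middle is > 0.0125, and either AFEQT has the smallest or Step 3 rejects nothing.

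**Error rate of the literal steps when the non-null effects are large.**

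- *AFEQT alone null, or mental alone null.* The other two p-values are near 0. If the null p-value is > 0.025, Step 1 accepts physical and Step 2 rejects AFEQT and mental; if it is ≤ 0.025, everything is rejected. The true null is rejected either way, so the error is 1.
- *AFEQT and mental null, or AFEQT and physical null.* The one real effect makes p(1) near 0, so H(1) = AFEQT is rejected at whichever step the procedure stops. The error is 1.
- *Physical alone null.* It is rejected only if the largest p-value is ≤ 0.025, so the error is 0.025.
- *Mental and physical null.* H(1) is correctly AFEQT, and the rest is the two-hypothesis Simes rule. The error is 0.025 for independent p-values.
- *All three null.* Any rejection is an error, so labels do not matter and Hommel's level holds.

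**Error rate at moderate effects.** This was simulated with 200,000 trivariate normal draws per setting and one-sided p-values. Assumptions not in the documents: standardized mean change d in each non-null score; pairwise correlation 0, 0.25 or 0.5; and n = 135, which is the follow-up count in SAP 7.1, not a count of completed questionnaires.

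| True nulls | d = 0.1 | d = 0.2 | d = 0.3 | d = 0.5 |
|---|---|---|---|---|
| AFEQT | 0.19–0.22 | 0.65–0.73 | 0.95–0.98 | 1.00 |
| mental | 0.02–0.06 | 0.29–0.37 | 0.80–0.82 | 1.00 |
| AFEQT + mental, or AFEQT + physical | about 0.12 | about 0.48 | about 0.86 | 1.00 |

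The other three configurations stay at or below 0.025 within simulation error. With H(i) attached to the sorted p(i), the error is 0.010–0.026 in all seven.

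**Disagreement when every score truly improves.** n = 135, AFEQT d = 0.5:

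| mental d, physical d | Trials naming different questionnaires |
|---|---|
| 0.2, 0.2 | 11–19% |
| 0.3, 0.3 | 4–6% |
| 0.4, 0.4 | about 0.3% |
| 0.4, 0.2 | at most 0.2% |
| 0.2, 0.4 | about 35% |

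At n = 100 the first row becomes 12–20%. In that first profile the AFEQT decision itself changes in about 0.01% of trials or fewer at n = 135. The disagreement is almost wholly over which SF-12 component is named.

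**The case against.** The strongest reply is that this is a slip of notation. SAP 6.5 names Hommel, cites the source paper, calls the method step-up and states its purpose. Bracketed subscripts usually denote ordered hypotheses, and the labelling sentence could be read as merely listing the family. Standard software returns Hommel-adjusted p-values that stay with their own tests, which is what SAP 6.2.4.1 requires. The large error rates arise only if a programmer declares a questionnaire improved on another's p-value.

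Most of this stands as evidence of intent. Protocol 17.4 has no labels, and SAP 6.8 reports "no changes to the statistical methods or principal features defined in the STOP AF First CIP version 5 are noted", although that sentence names a different study and so carries less weight. A program that applies SAP 6.2.4.1 or standard Hommel is unaffected.

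It does not rescue the text. The labelling sentence replaces the ordering convention with named hypotheses, and listing them in order is its more natural reading. The steps are the SAP's explicit algorithm, and followed exactly they give wrong answers. SAP section 8 requires independent programming only for the primary objectives, so the secondary analysis need not receive that check.

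**Conclusion.** The concern holds. SAP 6.5 states a wrongly indexed decision rule that contradicts the adjusted p-value criterion in SAP 6.2.4.1. The thresholds are right, and standard Hommel is very likely what is meant.

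The practical size depends on programming. With standard Hommel there is no effect. With literal steps, strong control of the 0.025 level is lost in four of seven null configurations, and the wrong questionnaire may be named even when all three improve. How often depends heavily on the assumed effects: from at most 0.2% to about 35% of trials in the profiles examined at n = 135.

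The scope is limited to the secondary objective, which SAP 6.5 tests only if the primary objectives are met. No primary test, estimate or sample size changes. The wording should be corrected before the secondary analysis is programmed.

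**What to change.** Replace the labelling sentence in SAP 6.5 with:

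> Let p(1) ≤ p(2) ≤ p(3) be the ordered p-values from the AFEQT, SF-12 mental and SF-12 physical tests, and let H(i) be the null hypothesis belonging to p(i).

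This still identifies the three hypotheses in the family. Keep Steps 1–3 and all thresholds. SAP 6.5 then agrees with SAP 6.2.4.1 and with the steps in Protocol 17.4. The cost is one sentence in the SAP.

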6.2.2.3. Analysis Methods

The probability of a subject achieving effectiveness success at 12 months (365 days) will be estimated using survival analysis, the Kaplan-Meier method. The standard error will be approximated using Greenwood's formula. A two-sided 95% log-log confidence interval for the probability will be constructed. For every treated subject, day 0 is defined as the day of the index cryoablation procedure. For subjects with treatment failure, the survival date will be set to the date of the treatment failure. For subjects without treatment failure through 12 months, those subjects will be censored at the last study contact date recorded on CRF which may include the last study visit, the exit date, or death date. If a subject without a treatment failure is lost to follow-up, the censoring date will be set to the last known study visit date.

For the component of the endpoint, documented AF/AT/AFL, if this documentation resulted from rhythm monitoring occurring at the 12-month visit within the 12-month visit window, the date of recurrence will be set to 365 days from the study ablation procedure so that these events will be counted as treatment failures in the 12-month Kaplan-Meier analysis. This objective will be analyzed in the mITT dataset: all enrolled subjects who have the Arctic Front Advance Cardiac CryoAblation Catheter inserted into vasculature will be included.

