6.2.3.3. Analysis Methods

The probability of a safety event at 12 months (365 days) will be estimated using survival analysis, the Kaplan-Meier method. The standard error will be approximated using Greenwood's formula. A two-sided 95% log-log confidence interval for the probability will be constructed.

For every treated subject, day 0 is defined as the day of the index cryoablation procedure. For subjects with a safety event, the survival date will be set to the date of the safety event. For subjects without a safety event, those subjects will be censored at the last study contact date recorded on CRF which may include the last study visit, the exit date, or death date. If a subject without a safety event is lost to follow-up, the censoring date will be set to the last known study visit date.

For subjects with a repeat ablation within 12 months, the start of the survival analysis will not reset. Day 0 will remain the day of the index cryoablation procedure. Safety events related to the repeat ablation procedure occurring on or prior to 365 days post the index cryoablation procedure will be counted as safety events and count against the primary safety objective. This objective will be analyzed in the mITT dataset: all enrolled subjects who have the Arctic Front Advance Cardiac CryoAblation Catheter inserted into vasculature will be included.

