7.1. Sample Size Determination for Efficacy Endpoint

Sample size was estimated using Proc Power in SAS 9.4. The calculation was designed to find the number of analyzed subjects required for a one-sided exact binomial test ($\alpha = 0.025$) to have 90% power in declaring the event rate significantly greater than the efficacy performance goal of 40%, when in fact the true rate of treatment success at 12 months is 54%. Attrition from enrollment to 12-month follow-up was assumed to be 10%, implying $150 * (1 - 0.1) = 135$ and $\text{floor}(165 * (1 - 0.1)) = 148$ subjects analyzed at one year for the PMA-S and PMDA datasets, respectively. The sample size calculation under these conditions can be replicated with the following SAS code:

```
proc power;
  ods output=Power=Power;
  test = Binomial;
  alpha = 0.025;
  power = 0.9;
  ntotal = 135;
  ncrit = 66;
  actual = 0.54;
  alpha = 0.0224;
  power = 0.899;
  ntotal = 148;
  ncrit = 72;
  actual = 0.54;
  alpha = 0.0202;
  power = 0.917;
run;
```

	N Total	Upper Crit Val	Actual Alpha	Power
(PMA-S)	135	66	0.0224	0.899
(PMDA)	148	72	0.0202	0.917

[figure not shown]
The power calculation outlined above is based on the binomial test, which is conservative compared to the power provided by the Kaplan-Meier methods (described in 6.2.2) that will actually be used. In the case of Kaplan-Meier analysis, attrition is partial: data is included for all subjects up until they exit the study, so only subjects who exit prior to day 0 (index ablation) will provide no information to the analysis.

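### The SAP merges or ignores demographic strata with fewer than five outcome events, so separate analysis depends on outcome; this matters mainly for safety

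*SAP*

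**What the plan says.** The subgroup text is printed after SAP section 6.5; the SAP Introduction places subgroup analyses in section 6.7. It states: "Demographic strata with <5 events will be combined with other strata if the resulting combination is still deemed analytically meaningful, or may be ignored"; the second branch reads in full "or may be ignored due to information sparsity". Age is split into quartiles, and on the comparison it says "The log-rank test will be utilized". On scope it says "Subgroup analyses will be performed in the same datasets in which the corresponding primary or secondary objectives are analyzed". Eight further subgroups, including BMI above 40 and the method of documenting persistent AF, are to be analysed in the same manner as the demographic variables, so the rule may reach them too.

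For both primary endpoints an event is a bad outcome. SAP 6.2.2.3: "For subjects with treatment failure, the survival date will be set to the date of the treatment failure". SAP 6.2.3.3: "For subjects with a safety event, the survival date will be set to the date of the safety event".

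The visible text gives no minimum number of subjects per stratum, no order of merging, and no criterion for choosing between merging and ignoring.

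**The concern.** The trigger is a count of outcomes. Of two strata of equal size, the one with more failures or complications is more likely to be analysed separately, and the one that did well is more likely to be merged or left out. Two distortions follow. The strata that stand alone have observed rates that are too high on average, because they were selected for having enough events. And a stratum with a raised complication rate may still fall short of five events and receive no separate analysis.

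The choice between merging and ignoring is made after events have been counted, in an unblinded single-arm study analysed by the sponsor's statisticians. At stake is the reading of safety by demographic group. The trial's success criteria are not at stake.

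**Working it through.** **Inputs.** True failure rate 46%, from the 54% success rate in SAP 7.1. True safety event rate 5% and performance goal 13%, from SAP 7.2. Planned size 150 treated, or 135 after 10% attrition (SAP 7.1). Age quartiles are therefore 150/4 = 37.5, about 38, or 135/4 = 33.75, about 34. All other stratum sizes below are assumptions, shown as a range. Follow-up is treated as complete, which simplifies the Kaplan-Meier setting.

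**The plan's own figures.** Exact binomial tails reproduce SAP 7.1 and 7.2:

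- Efficacy, N = 135, at least 66 successes: alpha 0.0224, power 0.899. N = 148, at least 72: 0.0202 and 0.917.
- Safety, N = 135, at most 9 events: alpha 0.0141, power 0.860. N = 148, at most 11: 0.0233 and 0.932.

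The SAP gives no figure for the strata rule itself.

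**The rule.** Let X be the events in a stratum of n subjects with true rate p, X ~ Binomial(n, p).

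- Chance of escaping the rule: P(X ≥ 5) = 1 − Σ C(n,x) p^x (1−p)^(n−x), summed over x = 0 to 4.
- Mean observed rate if it escapes: Σ (x/n) P(X = x) over x ≥ 5, divided by P(X ≥ 5).
- Lowest rate that can escape: 5/n.

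**Safety, worked for an age quartile of 38 at 5%.** The probabilities of 0 to 4 events are 0.1424 + 0.2848 + 0.2773 + 0.1751 + 0.0807 = 0.9603. The chance of escaping is 1 − 0.9603 = 0.0397. The lowest rate that can escape is 5/38 = 13.2%.

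| n | escapes | mean observed if it escapes | mean observed if caught | lowest rate that can escape |
|---|---|---|---|---|
| 34 | 2.6% | 15.6% | 4.7% | 14.7% |
| 38 | 4.0% | 14.1% | 4.6% | 13.2% |
| 45 | 7.3% | 12.1% | 4.4% | 11.1% |
| 50 | 10.4% | 11.0% | 4.3% | 10.0% |
| 75 | 32.1% | 7.9% | 3.6% | 6.7% |
| 105 | 60.8% | 6.3% | 2.9% | 4.8% |

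With two strata of 75, both escape in about 0.321 × 0.321 = 10% of trials. If a stratum's true rate is doubled to 10%, it is still caught in 67% of trials at n = 38, 53% at n = 45 and 12% at n = 75.

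**Efficacy at 46% failure.** For n = 8 the probabilities of 0 to 4 failures are 0.0072 + 0.0493 + 0.1469 + 0.2503 + 0.2665 = 0.7202, so the stratum escapes in 28% of trials.

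| n | escapes | mean observed failure if it escapes |
|---|---|---|
| 8 | 28% | 68% |
| 10 | 52% | 58% |
| 12 | 72% | 53% |
| 15 | 89% | 49% |
| 20 | 98.5% | 46% |
| 34–38 | nearly 100% | 46% |

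The dependence on outcome at a fixed small size is steep: at n = 10, a stratum with a true failure rate of 25% escapes in 8% of trials and one with 75% in 98%.

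**The case against.** The strongest defence is that the sentence may be about testing only. It sits beside the log-rank and Tukey text, and SAP 6.3 uses the same five-event example explicitly to skip heterogeneity tests while still promising a table by endpoint. Log-rank information does depend on events, so an event threshold for a p-value is sound. The opening of the subgroup section is missing from the available text and could hold a size rule or a commitment to descriptive tables. This stands as a reason not to claim that results will be withheld from the report. It does not remove the point: the sentence as written speaks of combining or ignoring strata, where SAP 6.3 speaks of testing.

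Four stronger readings are tempting, and the documents do not support them:

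- *A small stratum's failure rate is overstated whenever it is analysed alone.* At 46% failure this holds only up to n = 10. At n = 12, 5/12 = 42% escapes the rule and lies below 46%.
- *For safety, strata stand alone only when events cluster in them.* A stratum of 105 reaches five events in 61% of trials at an unremarkable mean of 6.3%.
- *A raised complication rate in one sex could be merged away.* Merging two sexes recreates the whole cohort, which is hardly a meaningful combination under the SAP's own condition. The branch that would apply is the permissive one, to ignore.
- *The rule was designed to select on outcome.* Nothing suggests this; the stated reason is sparse information.

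It is also fair that no success criterion in the visible text depends on these subgroups.

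**Conclusion.** The point holds with limited scope. Applied as written, the rule makes separate analysis of a demographic stratum depend on its outcome.

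For safety the effect is large in strata of the size the SAP itself creates: an age quartile of about 38 escapes in about 4% of trials, and only with an observed rate above the 13% goal. It is moderate at 75 and smaller at 105. For efficacy it matters for strata of about 15 or fewer and is negligible from about 20, so efficacy by age quartile is unaffected. The documents do not show that such small strata will occur. The pooled primary analyses are unaffected.

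The figures rest on the SAP's planning rates, complete follow-up, and assumed sizes for every stratum other than the age quartiles. Events are read as treatment failures or safety events; the word has no evident meaning for the quality-of-life scores, although the subgroup text also covers the secondary objective. Whether the rule governs display or only testing cannot be settled from the available text, and the SAP should say which.

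**What to change.** Amend the subgroup text in three respects:

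1. Define the strata, and any merging with its order, by number of treated subjects, fixed before outcomes are seen.
2. For every stratum so defined, report n, the number of events, and an estimate with a 95% confidence interval for each primary endpoint.
3. Use the fewer-than-five-events limit only to withhold the log-rank p-value, in line with how SAP 6.3 limits heterogeneity testing. State whether the same applies to the eight further subgroups.

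Retention then no longer depends on outcome, so the expected observed rate in a reported stratum equals its true rate: 5% rather than 14% for safety in a quartile of 38, and 46% rather than 58% for efficacy failure at n = 10.

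The cost is SAP wording and some extra table rows, with no new data. The drawback is wide intervals in small strata, and any cut-off on subjects is a judgement: 10 subjects at 5% give only 10 × 0.05 = 0.5 expected safety events.
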